#### 2. Basic and additional parameters under study

#### 2.1.Basic safety parameters:

- 1. The frequency of AE and/or SAE;
- 2. Overall assessment of the treatment tolerability by the investigator and the patient;
- 3. The main parameters of vital signs (HR, BP, RR, body temperature)
- 4. Results of physical examination;
- 5. Results of laboratory and instrumental examination.

Separately it is planned to evaluate the cumulative (in the framework of a double-blind and open study) frequency of the most likely complications associated with periprocedural or temporary postprocedural (no more than 72 hours) pain or burning. These NSAIDs can be stopped with paracetamol or non-steroidal anti-inflammatory drugs permitted by the Protocol.

Other possible side effects and complications of special interest related to the method of administration by intra-articular injection:

- pain or swelling at the injection site, feeling of bursting, burning, arthralgia, effusion in the joint, synovitis, aseptic acute arthritis;
- infections (pyogenic arthritis, direct infection of the joint at infectious diseases, osteomyelitis, sepsis, etc.);
- subcutaneous neuropathies, drug-induced vascular embolism.

It is assumed that the AEs are divided into groups: somatic AEs and AEs associated with the pathology of the target joint, as well as the frequency of both these groups, as well as each AE according to the following classification:

- Very common  $\geq 10\%$ ;
- Common (frequent) < 10%, but  $\geq$  1%;
- Uncommon < 1%, but  $\ge 0.1\%$ ;
- Rare < 0.1%, but  $\ge$  0.01%;
- Very rare < 0.01%.

#### The main parameters of the effectiveness of the studied MD:

Change in the overall score on the WOMAC scale (WOMAC-T) at Visit 3 (week 13), Visit 5 (week 25) compared to the basal value at Visit 0 (screening) of the open study and compared to the basal value at Visit 1 (week 1) of the IA/PAAG-SI/OA/2019 study;

- Change in the pain subscale score (WOMAC-A) on Visit 3 (week 13), Visit 5 (week 25) compared to the basal value on Visit 0 (screening) of the open study and compared to the basal value on Visit 1 (week 1) of the IA/PAAG-SI/OA/2019 study;
- Change in the score for stiffness subscale (WOMAC-B) and functional performance (WOMAC-C) at Visit 3 (week 13), Visit 5 (week 25) compared to the basal value at Visit 0 (screening) of open study and compared to the basal value at Visit 1 (week 1) of the study IA/PAAG-SI/OA/2019;
- The change in the severity of pain in the target knee on a 100-mm visual analogue scale (100 mm VAS) at Visit 2 (week 1), Visit 3 (week 13), Visit 5 (week 25) compared to the basal value at Visit 0 (screening) open safety study and compared to the basal value at Visit 1 (week 1) study IA/PAAG-SI/OA/2019;
- Evaluation of the effectiveness of treatment by the patient, parameter (on a scale from 1-clear deterioration to 6 - significant improvement) on Visits 3 and 5 (parameters OEP-w13 and OEPw25, respectively);
- Evaluation of the effectiveness of treatment by the investigator, parameter (on a scale from 1clear deterioration to 6-significant improvement) on Visits 3 and 5 (parameters OEI-w13, OEIw25, respectively);
- Assessment of the total number of paracetamol tablets taken (one tablet = 500 mg) starting from Day 1 at Visit 3 and 5 (parameters PARACETAMOL-w13 and PARACETAMOL-w25, respectively);
- Assessment of the total number of NSAID tablets taken starting from Day 1 at Visits 3 and 5 (parameters NSAID-w13 and NSAID-w25, respectively);
- 9. The parameter JSN of the target knee joint at Visit 5 of the open study compared to the basal value on Visit 0 of the IA/PAAG-SI/OA/2019 study retrospectively.

All performance parameters will be analyzed among all patients included in open study no. IA/PAAG-SI/OA/2020, as well as in subgroups of patients:

- who received only one course of injections in the placebo-controlled study IA/PAAG-SI/OA/2019;
- those who received two courses of therapy both in the placebo-controlled and at Visit 1 (and according to their indications at Visit 2) of the open study
- those who received two courses of therapy both in the placebo-controlled and at Visit 3 (and according to their indications at Visit 4) of the open study

### 3. Description of statistical methods

#### **3.1.** Description of statistical methods to be used

Statistical analysis will be carried out using specialized software, the selection of which will be carried out during the preparation of the statistical analysis plan.

Continuous (quantitative) data will be presented using the number of observations, arithmetic mean, 95% confidence interval (CI) for mean, standard (mean-square) deviation, median, interquartile range (25th and 75th centile), minimum and maximum.

Qualitative data (ordinal, nominal) will be presented using absolute frequencies (number of observations), relative frequencies (percent) and 95% CI.

Unless otherwise specified in the statistical analysis plan, statistical tests will be two-sided with a 5% confidence level.

The medical history and AEs will be encoded using the MedDRA classifier in the current version. Concomitant and prior therapy will be encoded using the ATX classifier.

This section briefly describes the planned analysis. The full analysis will be described in the statistical analysis plan.

#### 3.1.1. Demographic data, baseline data, and follow-up data.

As part of this open continuation study, an initial (on Visit 0) assessment of parameters similar to those for the double – blind IA/PAAG-SI/OA/2019 study will be performed, and data from the group originally included in the IA/PAAG-SI/OA/2019 study that received the medical device under study and the group that was included in the current open study will be compared. This comparison will be performed using descriptive statistics.

In addition, the initial characteristics will be compared depending on the actual distribution into the following subgroups:

- who received only one course of injections in the placebo-controlled study IA/PAAG-SI/OA/2019;
- those who received two courses of therapy both in the placebo-controlled and at Visit 1 (and as per the indications at Visit 2) of the open study;
- those who received two courses of therapy both in the placebo-controlled and at Visit 3 (and as per the indications at Visit 4) of the open study.

For comparison between these subgroups, variance analysis (for quantitative parameters) or the "Chisquare" criterion (for qualitative parameters) will be applied, followed by the application of multiple comparison criteria (if necessary).

#### 3.1.2. Analysis of safety parameters

In this study, the main parameters are safety parameters:

- 1. The frequency of AE and/or SAE;
- 2. Overall assessment of the tolerability of therapy by the investigator and the patient;
- 3. The main parameters of vital activity (heart rate, blood PRESSURE, body temperature, BDD);
- 4. Results of physical examination of the knee joint;
- 5. Results of laboratory and instrumental examination.

In addition, it is planned to evaluate the cumulative (in the framework of a double-blind and open study) frequency of the most likely complications associated with periprocedural or temporary postprocedural (no more than 72 hours) pain or burning.

Other possible side effects and complications of special interest related to the method of intra-articular injection will also be presented separately:

- pain or swelling at the injection site, feeling of bursting, burning, arthralgia, effusion in the joint, synovitis, aseptic acute arthritis;
- infections (pyogenic arthritis, direct infection of the joint at infectious diseases, osteomyelitis, sepsis, etc.);
- subcutaneous neuropathies, drug-induced vascular embolism.

It is planned to analyze the safety parameters for all included patients (safety population or FAS) using descriptive statistics, as well as in the following subgroups:

- those who received only one course of injections in the placebo-controlled study IA/PAAG-SI/OA/2019;
- those who received two courses of therapy both in the placebo-controlled and at Visit 1 (and as per the indications at Visit 2) of the open study;
- those who received two courses of therapy both in the placebo-controlled and at Visit 3 (and as per the indications at Visit 4) of the open study.

For comparison between these subgroups, variance analysis (for quantitative parameters) or the "Chisquare" criterion (for qualitative parameters) will be applied, followed by the application of multiple comparison criteria (if necessary).

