Patients who signed the informed consent form to participate in an open study IA/PAAG-SI/OA/2020 to evaluate the safety and effectiveness of MD NOLTREXTM, in the case when pain in the target knee joint in the study IA/PAAG-SI/OA/2019 remained the same or increased (on a 100-mm visual analogue scale [VAS]) compared to the rating at Visit 1 of the study IA/PAAG-SI/OA/2019 (or if a decrease in pain severity is less than 40— compared to the rating at Visit 1 of the study IA/PAAG-SI/OA/2019), will receive the injection of MD NOLTREXTM in the target knee (Group A). MD will be administered in accordance with the instructions for use of MD NOLTREXTM: 4.0 ml per injection (2.5 + 1.5 ml, or 2.0 + 2.0 ml from two syringes through one needle [one puncture]) at intervals of one week. The course in an open study is a maximum of 2 injections (the first - at Visit 1, the second - at Visit 2). The number of injections is determined by the doctor depending on the stage of gonarthrosis and the clinical response. In order to avoid overfilling the joint with dense slowly resorbable material, at the good clinical result (reducing the pain severity on a 100 mm VAS by Visit

2 by more than 40— compared to the basal level in the open study[1]), the course of injections will be discontinued.

Patients included in the open part of the study, who have the severity of pain in the target knee joint at the time of inclusion in the open part of the study decreased by 40— or more compared to the assessment on Visit 1 of the IA/PAAG-SI/OA/2019 study, or those who cannot be re-injected with MD NOLTREXTM, a re-injection of MD NOLTREXTM will not be performed on Visits 1 and 2 of the open study (Group B).

A repeated course of MD NOLTREXTM injections in an open study is not possible if any of the following criteria are met:

- 1. Documented intolerance of the studied MD NOLTREXTM;
- 2. Active inflammation in the target knee joint (edema, hyperemia, effusion) at the time of inclusion in the study;
- 3. Inflammatory diseases of the skin and soft tissues in the area of the intended introduction of the studied MD into the target joint;
- 4. History of venous thrombosis and thromboembolism;
- 5. Deviations from the norm in the coagulogram (activated partial thromboplastin time [APTT], prothrombin time [PT], prothrombin index, fibrinogen);
- 6. Hemophilia and other hemorrhagic diatheses, as well as taking anticoagulants and disaggregants;

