- Inflammatory changes in clinical blood analysis (leukocytosis, increased erythrocyte sedimentation rate [ESR]);
- 8. Deviation from the norm (in accordance with the standards of the local laboratory) of the number of platelets;
- 9. Type 1 or type 2 diabetes;
- 10. Acute infectious diseases or infectious exacerbations of chronic diseases (including respiratory tract infections) during the month prior to inclusion in the study.

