## 1.1 General provision

#### 1.1.1 Justification of selection of the clinical study type

An open-label intervention study in one group with OA patients who received a single course of injections of the NOLTREXTM medical device as part of the IA/PAAG-SI/OA/2019 study.

The open nature of the study in one group is determined by the main purpose of the study - to assess the safety of MD NOLTREXTM with a single or repeated course of use. It is assumed that continued monitoring of patients in the placebo group will not lead to the identification of new AEs, the frequency of which should be compared with the frequency in the active therapy group, and is connected to unethical restriction of patients in the placebo group from the possibility to use potentially effective synovial fluid endoprostheses.

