# **3.3.** Planned number of participants in a clinical trial study based on the sample size

This open-label MD NOLTREXTM safety assessment study includes eligible and non-eligible patients who received MD NOLTREXTM as part of the IA/PAAG-SI/OA/2019 study. Therefore, no formal calculation of the sample size was performed. The maximum expected number of study participants is the number of patients who were randomized to the MD NOLTREXTM group in the IA/PAAG-SI/OA/2019 study, i.e. 72 patients.

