## 3.4. Applicable level of significance

Statistical analysis of all the presented efficacy and safety parameters will be carried out at a 5% significance level, using two-way versions of statistical criteria.

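### The one-course subgroup merges patients still doing well with patients barred from re-injection, so comparisons of one course with two are confounded by contraindication as well as by response

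*SAP*

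**What the plan says.** The SAP (1.1.1) gives the main purpose as safety "with a single or repeated course of use".

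The protocol's study design section assigns patients to Group B, with no injection at Visits 1 and 2, by either of two routes. In the first, pain in the target knee has "decreased by 40— or more compared to the assessment on Visit 1 of the IA/PAAG-SI/OA/2019 study" (the percent sign was lost in the text; the Visit 3 rule prints it as 40%). The second route is joined on directly: "or those who cannot be re-injected with MD NOLTREXTM". Ten criteria bar a repeated course. Among them are "Documented intolerance of the studied MD NOLTREXTM", a history of venous thrombosis, an abnormal coagulogram and "Type 1 or type 2 diabetes". At Visit 3, Group B patients whose pain meets the criterion are injected only if no bar applies.

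The SAP then forms three subgroups: "those who received only one course of injections in the placebo-controlled study" (the one-course subgroup), those re-injected from Visit 1, and those re-injected from Visit 3. It uses them for baseline characteristics (3.1.1), safety (3.1.2) and efficacy (3.1.3). Safety is compared by analysis of variance or chi-square without covariates. The only adjustment in the plan is baseline WOMAC, for WOMAC endpoints. Under SAP 3.4, testing "will be carried out at a 5% significance level, using two-way versions of statistical criteria". On size, SAP 3.3 says "Therefore, no formal calculation of the sample size was performed" and gives a maximum of 72.

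**The concern.** The one-course subgroup is defined by what was not given, whatever the reason. A patient who did not need a second course and a patient who needed one but could not have it are counted together. Patients in the re-injected subgroups, by contrast, had no bar when they were injected.

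Some bars are markers of general illness. Device intolerance is itself a safety outcome, and here it helps decide which subgroup a patient joins. If barred patients have more AEs for reasons unrelated to the number of courses, the one-course rate rises and a second course looks safer than it is. For efficacy, the one-course mean describes neither the durability of one course nor the course of untreated relapse.

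**Working it through.** **Tracing patients to subgroups**

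| Pain criterion met (Visit 0 or Visit 3) | Bar applies | SAP subgroup |
|---|---|---|
| No | No | One course |
| No | Yes | One course |
| Yes | Yes, and not cleared | One course |
| Yes, at Visit 0 | No | Re-injected from Visit 1 |
| Yes, at Visit 3 | None at Visit 3 (possibly one at entry) | Re-injected from Visit 3 |

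1. *Can barred patients enter?* Yes. Intolerance, thrombosis history, abnormal coagulogram and diabetes are bars but not non-inclusion criteria. The sample-size text says that both eligible and non-eligible patients are included.
2. *Do they stay?* Intolerance, thrombosis history and diabetes will not normally clear by Visit 3, so these patients remain in the one-course subgroup. A patient with a temporary bar at entry can move to the Visit 3 subgroup, which is then mixed too.
3. *Does the analysis separate them?* No. SAP 3.6 and the protocol's blinding section describe the subgroups as formed by need for treatment. Barred patients with pain had that need, yet are grouped with patients who did not.
4. *Efficacy.* On the 100 mm VAS, measured from Visit 1 of the 2019 study, the two kinds of patient lie on opposite sides of the 40% threshold by definition at the visit where the criterion was met. Their pooled mean depends on the mix.

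**Hypothetical size for safety**

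The plan gives no AE rate, barred share or subgroup size, so there is no figure to reproduce and every input here is an assumption. Let p be the AE risk in one-course patients without a bar, p_b the risk in barred patients, and s the barred share of the subgroup. The two re-injected subgroups are taken together.

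- One-course rate = (1 − s)·p + s·p_b
- Apparent difference (repeated minus single) = true difference − s·(p_b − p)

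With p = 20%:

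| s | p_b | One-course rate | Apparent difference, true 0 | Apparent difference, true +10 points |
|---|---|---|---|---|
| 10% | 40% | 18 + 4 = 22% | −2 | +8 |
| 25% | 40% | 15 + 10 = 25% | −5 | +5 |
| 50% | 40% | 10 + 20 = 30% | −10 | 0 |
| 10% | 60% | 18 + 6 = 24% | −4 | +6 |
| 25% | 60% | 15 + 15 = 30% | −10 | 0 |
| 50% | 60% | 10 + 30 = 40% | −20 | −10 |

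If p_b equals p there is no distortion, and if p_b is below p the sign reverses.

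**Which events are affected**

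- *General AEs:* the formula applies as it stands.
- *Cumulative procedural pain or burning over both studies:* a reaction in 2019 that led to an intolerance record would count in the one-course subgroup. In the extreme case of p_b = 100%, the rates are 18 + 10 = 28%, 15 + 25 = 40% and 10 + 50 = 60%.
- *Injection-related events in the open study:* nobody in the one-course subgroup is injected in this study, so its composition matters little.

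**The case against.** The strongest reply has four parts.

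**This is not the main safety analysis.** SAP 3.1.2 first plans descriptive safety in all included patients, and SAP 1.1.2 names the 2019 placebo data as the control. No confirmatory hypothesis is stated. This stands, and a reader who took the subgroup test for the study's principal contrast would go too far. Still, it is the only between-group safety comparison with a stated method, and it bears on the stated purpose.

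**Size and direction are unknown.** This stands. A reader might infer that harm from a second course is being hidden; the documents do not show that. A reader might also size the barred share from laboratory reference ranges. If each range covers 95% of healthy people and tests are independent, the chance of at least one barring value is 1 − 0.95⁵ × 0.975² = 26.4%, or 1 − 0.95⁴ × 0.975² = 22.6% with prothrombin time and index counted once. That describes healthy people, who would have no raised AE rate, so it cannot be joined to a high p_b. Nor is it the share of the one-course subgroup, which also depends on how many patients relapse. If the 2019 study already excluded these conditions, few may be barred.

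**Little could be detected anyway.** With an assumed 36/36 split of the maximum 72, 20% against 30% has about 16% power. True, but the estimates will be reported and read whatever the test says.

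**The plan partly discloses the problem.** SAP 3.1.1 compares baseline characteristics across the same subgroups, SAP 3.6 concedes that they follow need, and joint inflammation and effusion are already non-inclusion criteria. This helps a reader see an imbalance, but contraindication is not mentioned and the two kinds of patient stay merged.

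**Conclusion.** The pooling follows directly from the protocol's allocation rules and the SAP's subgroup definitions and needs no assumption. The comparisons of one course with two are confounded by contraindication in addition to response, and the one-course efficacy mean has no clear meaning.

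The consequence is less certain. Masking of harm is plausible for general AEs and for the cumulative endpoint over both studies, and much less so for injection-related events in the open study. The shifts of 2 to 20 points in the first table rest wholly on assumed rates and shares and are not estimates for this trial. Confounding by response would remain without a single barred patient. The point should be fixed because the change is cheap and makes the subgroup interpretable; it does not invalidate the descriptive safety analysis in all patients.

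**What to change.** In SAP 3.1.1 to 3.1.3:

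- Report the one-course subgroup in two parts. **1a:** pain criterion not met at Visit 0 or at Visit 3. **1b:** criterion met at either visit but not re-injected, with the reason (barred, and by which criterion, or declined). Use the Visit 0 VAS for entry, since none is listed at Visit 1 of the open study. State how patients who leave before Visit 3 are classified.
- Flag any bar within 1a, because responders can carry one too, and flag Visit 3 patients who were barred at entry.
- Base the comparison of single with repeated course on patients without a bar. Label it non-causal, because 1a still differs from the re-injected patients by response.
- Keep barred patients in the all-patient safety tables, so that their events are not lost.
- Confirm that the reason for no re-injection is captured in the eCRF or can be derived from VAS, history, concomitant therapy and laboratory data. No listed visit procedure records it explicitly.

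The cost is SAP wording, plus possibly one eCRF field or a derivation rule. Sample size and treatment are unchanged. The downside is that 1b may be small and only descriptive. The split should be fixed before results are seen, since a later one would be post hoc.

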At Visit 3 additional evaluation will be conducted to assess the feasibility and possibility of reinjections with MD NOLTREXTM among patients of group B. If at Visit 3 of the open study pain remains the same in the target joint of the study IA/PAAG-SI/OA/2019 or increases in intensity (as per 100-mm VAS) in comparison with the assessment at Visit 1 of the study IA/PAAG-SI/OA/2019 (or if a decrease in pain severity is less than 40% when compared to the rating at Visit 1 of the study IA/PAAG-SI/OA/2019), in the absence of the above criteria for non-treatment with the studied MD, at Visit 3 of open study the injection of MD NOLTREXTM into the target knee joint will be performed. MD will be administered in accordance with the instructions for medical use of MD NOLTREXTM: 4.0 ml per injection (2.5 + 1.5 ml, or 2.0 + 2.0 ml from two syringes through one needle [one puncture]) once or twice at intervals of one week. The treatment course in the framework of an open study among patients of Group B is a maximum of 2 injections (the first - at Visit 3, the second - at Visit 4). The number of injections is determined by the doctor depending on the stage of gonarthrosis and the clinical response. In order to avoid overfilling the joint with dense slowly resorbable material, at the good clinical result (reducing the pain severity on a 100 mm VAS by Visit 2 by more than 40— compared to the basal level in the open study[1]), the course of injections will be discontinued. The open nature of the study in one group is determined by the main purpose of the study - to assess the safety of MD NOLTREX[™] with a single or repeated course of use. Placebo safety data at the 6-month point (visit 5) in the IA/PAAG-SI/OA/2019 study will be used as a control. It is assumed that continued monitoring of patients in the placebo group will not lead to the detection of new adverse events (AE), the frequency of which should be compared with the frequency in the active therapy group, and is connected to unethical restriction of patients in the placebo group in the possibility of using potentially effective synovial fluid endoprostheses.

The open study provides follow-up of patients for 6 months (up to 25 weeks from Visit 1).

Thus, the maximum duration of participation in the study for one patient will be a maximum of 172 days.

Patient visits

Visit 0 (Day 0, -24 h -0 h, screening)

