Visit 1 (Week 0, Day 1, start of treatment)

- Measurement of the body weight;
- Collection of complaints and anamnesis;
- Registration of concomitant therapy;

- Assessment of the main vital signs (BP, HR, RR, body temperature);
- Physical examination of joints;
- Evaluation of inclusion/non-inclusion criteria;
- Injection of the studies MD into the cavity of the target joint (only for group A patients who are shown to receive the injection in accordance with the criteria specified in the Protocol);
- Registration of AE and SAE;
- Evaluation of exclusion criteria.

Every 2 weeks between Visit 1 and Visit 3 (weeks 3, 5, 7, 9 and 11), telephone contacts are made with the patient to clarify complaints, AE and the need for taking paracetamol or NSAIDs for the past 2 weeks. If AE is detected, or the need to take paracetamol or NSAIDs more than 4 days a week in each of the consecutive 2 weeks, the patient is invited to the clinic for an unscheduled Visit or a Visit to prematurely complete participation in the study (depending on the reason for the visit).

Visit 2 (Week 1, Day 8, treatment and follow-up) - as indicated

Only patients who received an injection of MD NOLTREXTM into the target knee joint on Visit 1 are eligible for Visit 2.

The following procedures must be performed during the visit:

- Measurement of the body weight;
- Collection of complaints and anamnesis;
- Registration of concomitant therapy;
- Assessment of the main vital signs (BP, HR, RR, body temperature);
- Physical examination of joints;
- Assessment of the severity of pain in the target knee joint using 100-mm VAS;
- Injection of the studied MD into the target joint cavity (only for patients of group A, in which the severity of pain in the target knee joint using 100 mm VAS did not decrease by 40% or more compared to the assessment on the Visit 0);
- Evaluation of the patient's diary;
- Return of the diary to the patient;
- Registration of AE and SAE;
- Evaluation of exclusion criteria.

Visit 3 (Week 13, Day 84 ± 2, treatment and follow-up)

- Measurement of the body weight;
- Collection of complaints and anamnesis;
- Registration of concomitant therapy;
- Assessment of the main vital signs (BP, HR, RR, body temperature);
- Physical examination of joints;
- Filling out algofunctional questionnaire WOMAC with an assessment of the subscales of pain (WOMAC-A), stiffness (WOMAC-B) and functional performance (WOMAC-C);

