- Physical examination of joints;
- Assessment of the severity of pain in the target knee joint using 100-mm VAS;
- Injection of the studied MD into the target joint cavity (only for patients of Group B, in which the severity of pain in the target knee joint using 100 mm VAS did not decrease by 40% or more compared to the assessment at Visit 3)
- Evaluation of the patient's diary;
- Return of the diary to the patient;
- Registration of AE and SAE;
- Evaluation of exclusion criteria.

Visit 5 (Week 25, Day 169 ± 2 , follow-up)

- Measurement of the body weight;
- Collection of complaints and anamnesis;
- Registration of concomitant therapy;
- Assessment of the main vital signs (BP, HR, RR, body temperature);
- Physical examination of joints;
- Radiography of the knee joints and documentation of parameters of joint space width (JSW) and joint space narrowing (JSN);
- Filling out algofunctional questionnaire WOMAC with an assessment of the subscales of pain (WOMAC-A), stiffness (WOMAC-B) and functional performance (WOMAC-C);

- Assessment of the severity of pain in the target knee joint using 100-mm VAS;
- Evaluation of the effectiveness of treatment by the patient, OEP parameter;
- Evaluation of the effectiveness of treatment by the investigator, OEI parameter;
- Clinical blood test (hemoglobin level, hematocrit, red blood cell count, white blood cell formula, platelet count, ESR);
- Biochemical blood test (glucose, ALT, AST, ALP, GGTP, total bilirubin, creatinine, uric acid, rheumatoid factor);
- Coagulogram (APTT, PT, prothrombin index, fibrinogen);
- General urinalysis (color, transparency, relative density, pH, glucose, protein, ketone bodies, urobilinogen);
- Evaluation of the patient's diary;
- Evaluation of the total number of paracetamol tablets taken (one tablet = 500 mg) using patient's diary, PARACETAMOL parameter;
- As per patient's diary, evaluation of the total number of NSAIDs allowed by the Protocol in case of paracetamol inefficiency (NSAIDs allowed by the Protocol in case of paracetamol inefficiency: diclofenac potassium tablets 50 mg, diclofenac sodium tablets 75 mg, naproxen tablets 500 mg, naproxen sodium tablets 550 mg, meloxicam tablets 7.5 mg, celecoxib tablets 200 mg), NSAID parameter;
- Registration of AE and SAE;
- Evaluation of exclusion criteria.

An unscheduled visit

The following procedures must be performed during the visit:

- Measurement of the body weight
- Collection of complaints and anamnesis;

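### SAP 3.1.2 compares AE frequency between subgroups fixed by treatment eventually received and does not tie AEs to the preceding course, so the single-versus-repeated-course comparison can be diluted or biased

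*SAP*

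**What the plan says.** The stated main purpose is the safety of the device after a single or repeated course (SAP 1.1.1 and 1.1.2). SAP 3.1.2 puts AE/SAE frequency first among the safety parameters. It analyses them descriptively in all patients and then in three subgroups: one course only (in the 2019 study), a second course from Visit 1, and "those who received two courses of therapy both in the placebo-controlled and at Visit 3". The rule that follows begins "For comparison between these subgroups, variance analysis (for quantitative parameters) or the" and goes on to name chi-square for qualitative parameters, with multiple comparisons if needed. SAP 3.4 sets a two-sided 5% level.

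No section gives an AE counting window, a rule based on onset date, or patient-time. The one time-linked item is procedural pain or burning lasting no more than 72 hours, and it is pooled over both studies. SAP 3.1 adds a caveat: "This section briefly describes the planned analysis".

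The Protocol's visit schedule places the second course of the third subgroup at "Visit 3 (Week 13, Day 84 ± 2, treatment and follow-up") and the end of follow-up at "Visit 5 (Week 25, Day 169 ± 2 , follow-up"). Under Study design, a Group B patient is injected at Visit 3 if "pain remains the same in the target joint of the study IA/PAAG-SI/OA/2019 or increases in intensity", or if it has fallen by less than 40% from the 2019 baseline, and if none of the listed bars applies. The bars include documented intolerance, inflammatory blood changes, and abnormal coagulogram or platelet results. The blood tests are repeated at Visit 3.

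**The concern.** There are two separate problems.

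**Dilution.** A patient in the Visit 3 subgroup spends about the first half of the open study having had one course only. If AEs are counted over the open study, those from that period enter a subgroup labelled as two-course. Any lasting effect of the second course is then averaged with time in which it could not act.

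**Selection.** The one-course and Visit 3 subgroups both come from Group B and are separated by what has happened up to Visit 3.
- Persistent knee pain moves a patient into the two-course subgroup, and the AEs of special interest include "pain or swelling at the injection site, feeling of bursting, burning, arthralgia, effusion in the joint, synovitis".
- New intolerance or a new laboratory abnormality keeps the patient in the one-course subgroup, as does withdrawal before Visit 3.

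The outcome being counted can therefore help decide the subgroup, in either direction. SAP 3.6 recognises that subgroups follow actual need for treatment, but uses this only to rule out imputation.

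At stake is the only comparison in 3.1.2 that addresses single versus repeated course. A chi-square result would not show whether a difference came from the device, the counting rule or the entry rule.

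**Working it through.** The plan has no sample-size or power figure to reproduce; 72 is a maximum. One timing check is possible. The latest Visit 5 is Day 171, and adding Day 0 gives 172 days, which matches the Protocol's maximum participation.

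**Inputs from the Protocol:** Visit 1 on Day 1, Visit 3 on Day 84 ± 2, Visit 5 on Day 169 ± 2. **Assumed, because the documents give no AE rates or re-injection shares:** a constant hazard, an AE risk over 168 days of 10%, 20% or 40% after one course, and the entry probabilities below.

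**1. Share of time before the second course.** (84 − 1)/(169 − 1) = 83/168 = 49%. Over the visit windows it runs from 81/170 = 48% to 85/166 = 51%. The remaining 85 days follow the second course.

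**2. Dilution of a lasting rate ratio r.** Apparent ratio = (83 + 85r)/168. For r = 1.5, 2 and 3 this gives 1.25, 1.51 and 2.01.

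**3. Absolute differences when r = 2.** With one-course risk p, the hazard is h = −ln(1 − p)/168.
- Difference after Visit 3 only: [1 − exp(−170h)] − [1 − exp(−85h)].
- Difference over the whole window: [1 − (1 − p)^1.506] − p.

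| p | After Visit 3 only | Whole window |
|---|---|---|
| 10% | 4.9 points | 4.7 points |
| 20% | 9.5 points (20.2% v 10.7%) | 8.5 points (28.5% v 20.0%) |
| 40% | 17.6 points | 13.7 points |

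The ratio is diluted clearly. The absolute difference changes little at 10% to 20% risk.

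**4. Selection within Group B, no true effect, p = 20%.** Early risk (83 days) b = 0.1044; late risk (85 days) a = 0.1068. Let s1 and s0 be the shares re-injected with and without an early AE, with s0 = 0.5.
- Visit 3 subgroup risk = [b·s1 + (1 − b)·s0·a] / [b·s1 + (1 − b)·s0].
- One-course risk = [b(1 − s1) + (1 − b)(1 − s0)a] / [b(1 − s1) + (1 − b)(1 − s0)].

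Suppose a fraction q of early AEs affects entry. On the barring route alone, half of those patients are barred or withdrawn, so their share re-injected is 0.25. On the pain route alone, their share is 0.9. Then s1 = q × (0.25 or 0.9) + (1 − q) × 0.5.

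| q | Barring route: s1, ratio | Pain route: s1, ratio |
|---|---|---|
| 0.25 | 0.4375, 0.90 | 0.60, 1.18 |
| 0.5 | 0.375, 0.81 | 0.70, 1.41 |
| 1 | 0.25, 0.65 | 0.90, 2.06 |

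With both routes at mid-range and every early AE relevant (25% barred, the rest re-injected at 70%), s1 = 0.75 × 0.70 = 0.525 and the ratio is 1.04.

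**5. Counting only from Visit 3 among Group B patients still in the study.** The same model gives a/a = 1.00 with no effect, and 0.2021/0.1068 = 1.89 for r = 2, whichever entry route acts. If patients differ strongly in AE proneness (gamma, variance 1, every early AE affecting entry, no true effect), it leaves 0.92 to 1.14, against 0.63 to 2.17 for the whole-window count.

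**6. Precision.** At an assumed 24 patients per subgroup, the chi-square has 11% power for 28.5% v 20.0% and 15% for 20.2% v 10.7%.

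**The case against.** The best defence is that 3.1.2 is silent rather than wrong. It states no AE counting window and does not name chi-square for AEs specifically, and SAP 3.1 says that a fuller analysis will follow. This stands in part: dilution is conditional on AEs being counted over the open study. But the subgroup definitions and the test for qualitative parameters are stated, AE frequency is the first parameter they apply to, and nothing elsewhere supplies an onset rule.

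Dilution is also narrow. It needs a hazard raised for the remaining 85 days, whereas the SAP calls procedural pain or burning the most likely complication. Such reactions are not diluted. This stands.

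A reader might infer from the outer figures, 0.65 to 2.06, that the comparison is grossly biased. The documents do not support that. Those figures need every early AE to alter entry, yet AEs are divided into somatic and target-joint groups, and a somatic AE need not change knee pain or a blood test. The trigger is pain at Visit 3, so an early pain AE that has resolved would not count. Group B has no open-study injection before Visit 3, which makes new intolerance or injection-related arthralgia less likely in that period.

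Finally, with at most 72 patients chance may exceed any of these biases. That is true, and is itself a reason not to rest on a significance test.

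**Conclusion.** The point holds as one of attribution. The 49% share follows from the visit schedule alone, and the dependence of entry on the patient's state at Visit 3 follows from the Protocol's own rules. Read over the open study, the planned subgroup comparison counts one-course AEs as two-course experience and can be biased in either direction within Group B.

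The size is not known. A lasting rate ratio of 2 would appear as about 1.5. The selection bias is modest if only some early AEs affect entry, and could be close to nil if the two routes offset each other. These figures rest on a constant hazard and, for selection, on the assumed 20% risk and re-injection shares.

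It would go too far to infer that the study's safety findings as a whole are unreliable. The all-patient AE tables do not depend on these subgroups, and neither does the planned use of the 2019 placebo data as control. It should be fixed because the affected comparison is the one in 3.1.2 that bears on single versus repeated use.

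**What to change.** Amend SAP 3.1.2 as follows.

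- (a) Assign each open-study AE by onset date to the most recent course, and count the Visit 3 subgroup's time before Visit 3 as one-course time.
- (b) By course, report patients with events and events per patient-time with 95% CIs. Report periprocedural events (72 hours or less) per injection.
- (c) Compare re-injected with not re-injected patients at Visit 3 only among Group B patients still in the study at that visit, counting AEs from Visit 3 on. Compare patients injected at Visit 1 with all of Group B over Visit 1 to Visit 3.
- (d) Present these comparisons descriptively in place of the chi-square test, and state that confounding by indication remains.

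The cost is SAP wording and slightly longer AE tables, with no new visits or assessments. Between Visits 1 and 3, "telephone contacts are made with the patient to clarify complaints, AE" every two weeks, and AEs are registered at Visit 3, so most earlier events can already be separated from later ones. The sponsor should check that the eCRF holds AE onset dates, since the documents do not list its fields. The change does not raise power.
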